7 METHODS AND STUDY PROCEDURES

7.1 Study sites and personnel

7.1.1 Selection of study sites

The study will be conducted at five sites, all of which have high mortality in children under age five years, quality-assured microbiology laboratories, little or no published data on causes of fever, and suitably qualified research teams and capacity: 1) Phonhong Vientiane Province, Lao Peoples' Democratic Republic; 2) Chikwawa, Malawi; 3) Yangon, Myanmar; 4) Manhiça, Mozambique; and 5) Harare, Zimbabwe. These sites have been selected because they fulfil the above criteria, and because there is substantial across-site variation in the prevalence of HIV and malaria (based on available data) and other endemic infectious diseases.

Within each participating country, the health facilities for this study will be selected on the basis of the following characteristics: interest and capacity of local researchers and public health authorities; accessibility from the collaborating research team's base; interest and capacity of the health facility staff; and patient numbers adequate to allow enrolment of the target sample size over the period of 12 months (to be extended at individual sites if required to meet sample size target). On the basis of current information and preliminary agreements, selected sites include: in Lao PDR, Phonhong Vientiane Provincial Hospital in Vientiane Province; in Malawi, Chikwawa District Hospital; in Mozambique, Manhiça's District Hospital (MDH) in Manhiça, and peripheral health posts of Maragra, Malavele, Palmeiras, Ilha Josina Machel, and Taninga; in Myanmar, Thanlyin District Hospital; in Zimbabwe, Harare and Parirenyatwa Hospital and two primary care clinics in Harare City. If for unforeseen reasons we are unable to conduct the evaluation at the specific facilities listed, alternative sites will be chosen to preserve the representative range of geography and epidemiology.

7.1.2 Personnel conducting protocol activities

For the purposes of this study, routine clinical care will be provided by the staff of participating health facilities, i.e., health workers who are employed by the health facility. Such health workers typically include physicians, clinical officers, nurses, laboratory

technologists or technicians, and other similar cadres of health care staff. In this protocol, these personnel are referred to as “health facility staff.”

Study-specific activities will be conducted by personnel hired for the purposes of the research study, i.e., individuals recruited by the organisation coordinating the study site. In this protocol, these personnel are referred to as “study staff.” Study staff typically will be individuals with clinical, laboratory, and/or social science training and with prior experience in clinical and/or social science research. Study staff will be trained in the protocol and relevant study procedures prior to the start of the study, and health facility staff will be informed of the study. At each site study staff will work with health facility staff to achieve the study goals while ensuring smooth continuation of care.

7.2 Study enrolment

7.2.1 Selection of patients for recruitment and enrolment

At each site, patients (or parents/guardians on behalf of minors) will be invited to participate in the study when they present with fever to the participating health facilities for care.

Health centre staff will work with study staff to identify patients who present with fever.

Study staff will screen and enrol participants according to the selection criteria listed in section 6. A total of 2400 patients will be enrolled at each site (see sample size calculations in section 11.3), with approximately half being outpatients and half inpatients. If a patient is enrolled as an outpatient but deteriorates clinically and is admitted to hospital within <24 hours after enrolment, the patient will be re-classified as an inpatient for study purposes. If a patient is enrolled as an outpatient and then admitted ≥ 24 hours after enrolment, s/he will remain listed as an outpatient for study data purposes.

Since the causes of fever are likely to be different in children and adults, enrolment will be stratified so that participants are enrolled in two age groups of approximately equal numbers: children aged two months (≥ 2 months) to <15 years, and those aged 15 years and older. In addition, so that results accurately represent the patient population at each site, site-specific recruitment strategies will be developed to achieve enrolment of a random sample of patients presenting throughout the day and week (including those presenting after hours or at weekends, who may come from areas further from the health facility, and/or have more severe presenting symptoms) and over the course of the 12-month

recruitment period. In each of the four categories defined by age and in-/outpatient status, 12 consecutive patients per week will be recruited. The day of the week that recruitment starts will be rotated. There may be slight variations on this strategy due to site specific constraints. The total number of patients presenting to the hospital with fever each day (or week), including those not in the study, over the course of the study period will be recorded.

Patients who are not enrolled in the study will be managed according to routine practice by health facility staff. For those patients who are screened and excluded, the reason for exclusion will be recorded, along with the patient's age, sex, and location of usual residence. At each site where HIV testing will be performed (i.e., where HIV prevalence in the general adult population is >1%), HIV counselling and testing is linked to an established treatment program. Other acute or chronic conditions are managed on-site as capacity allows, or referred to a higher level of the health care system according to local guidelines.

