7.5.1 Selection and recruitment of community controls

To define the catchment area for outpatients and community controls, existing data and pilot data from each site will be combined to define an area around the study facility in which approximately 80% of outpatients live. Residing within this area will be a selection criterion for FIEBRE outpatients (section 6). Community controls will be recruited within this area, individually matched to participating outpatients.

During each month of the study at each site, half of the outpatients will be selected at random (or by taking every second outpatient in chronological order of presentation). For each of these a community control will be found matched on age (within bands: ≥ 2 to < 6 months, ≥ 6 to < 12 months, ≥ 1 to < 3 years, ≥ 3 to < 5 years, in 5 year bands up to age 24, and in 10 year bands at older ages), sex and place of residence. At sites where the study team's capacity enables them to recruit a larger number of controls, controls will be matched to a larger proportion of enrolled outpatients. For example, if capacity allows, one control will be found for every outpatient; or controls will be found for more than half of the outpatients, e.g. for a random sample of three-quarters of enrolled outpatients (or by selecting every second, third, and fourth outpatient, in chronological order of presentation). This approach will allow us to enhance the precision of estimates for specific primary objective 1 and specific secondary objective 1 (see also section 11.1 below on quantitative outcome measures and analysis).

Community controls will be recruited and enrolled if they, or their parents/guardians, provide informed consent.

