11.1 Quantitative outcome measures and analysis

Listed by study objective:

- 1) To determine the treatable and/or preventable causes of fever in children and adults presenting as outpatients, and among those admitted to hospitals, in areas represented by the study sites;

For outpatients the attributable fraction (AF) will be calculated for each pathogen or group of pathogens. This will be done separately for each site and age stratum. For each group of patients, the odds ratio (OR) for the association between each pathogen and fever will be calculated by comparing cases and controls. Logistic regression will be used to calculate the odds ratio. In order to take the matched design into account, strata based on geographical location and season will be defined at each site and the analysis will be adjusted for age, sex and stratum. Since cases and controls are recruited at a constant rate throughout the year but fever incidence is likely to vary by season, the analysis will be weighted by the proportion of patients included in the study of the total number of cases seen at the study

site in the given season. AF will then be calculated as $AF_A = p_A(1-OR_A)$. Confidence intervals will be calculated in an appropriate way, e.g. bootstrapping or delta method.

For inpatients, first the distribution of diagnoses in each site will be tabulated for all inpatients in the study. Then a second analysis to calculate AFs will be carried out for inpatients, but this will be restricted to inpatients who come from the same geographical area as the controls. The calculation of AFs for inpatients may be dropped if insufficient numbers of in-patients come from the same area as the controls.

- 2) To determine how fever aetiology varies according to patient age, level of the health system, geographical area, local malaria and HIV prevalence, and other risk factors;

Stratified analyses will be carried out as above to estimate the AF for sub-groups of patients.

- 3) To determine the prevalence and spectrum of antimicrobial resistance among bacterial pathogens identified in clinical specimens from febrile patients;

At each site the proportion of bacterial pathogens with antimicrobial resistance defined by standardized criteria will be calculated. The proportion of common organisms demonstrating resistance to a standard panel of antibiotics will be reported.

Specific secondary objectives:

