1) To generate data on incidence of specific infections among study participants, and therefore contribute key data on disease burden for some infections that are not counted in current “global burden of disease” estimates;

For an area whose population size is known, a health utilization survey will be used to estimate r , the proportion of fevers for which treatment was sought at a study centre. The total number of cases seen at the study site from the defined population will be multiplied by $1/r$, to obtain the total cases in a year from the defined population. This will be divided by the size of the population to estimate incidence. Incidence of fever caused by specific pathogens will be calculated by multiplying the incidence by the AF for that pathogen.

3) Evaluation of available biomarker assays to assess their performance and potential utility in fever case management in the study areas;

The sensitivity, specificity, and positive and negative predictive value of each biomarker will be estimated.

4) To generate data to support the development of new fever case management algorithms which may be evaluated in future studies;

The association between the presence of pathogens with predefined clinical and other variables will be examined.

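### The fever count in Protocol 7.2.1 is a single total at the hospital, so it does not supply weights that fit the age-stratified outpatient AF analysis, nor, directly, the incidence numerator

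*Protocol*

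**What the plan says.** **The count.** Protocol 7.2.1 sets a fixed quota: "In each of the four categories defined by age and in-/outpatient status, 12 consecutive patients per week will be recruited". Beside it stands the only fever denominator in the document: "The total number of patients presenting to the hospital with fever each day (or week), including those not in the study". No breakdown is named.

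**Patients not enrolled.** The same section adds: "For those patients who are screened and excluded, the reason for exclusion will be recorded", together with "age, sex, and location of usual residence". This covers people who were screened. Nothing requires screening of patients who present once the week's quota is full.

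**First use, the weights.** For primary objective 1, section 11.1 estimates outpatient AFs separately for each site and age stratum. Because recruitment is constant while fever incidence is seasonal, it adds a weight: "the analysis will be weighted by the proportion of patients included in the study of the total number of cases seen at the study" (that is, per site and season).

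**Second use, incidence.** For secondary objective 1, section 11.1 states: "The total number of cases seen at the study site from the defined population will be multiplied by" (the multiplier is the reciprocal of r, the share of fevers brought to a study centre). The result is divided by the population size, and then multiplied by the pathogen's AF. Section 7.5.4 asks for an estimate of all fever cases presenting to the study sites.

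**Facilities and area.** Section 7.1.1 lists one hospital each in Laos, Malawi and Myanmar. Mozambique has a district hospital plus five health posts, and Zimbabwe has hospital care plus two primary care clinics. Section 7.5.1 defines the outpatient catchment as "an area around the study facility in which approximately 80% of outpatients live".

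**The concern.** With a fixed weekly quota per category, the fraction sampled depends on how many people present in that category. A total that mixes children with adults and outpatients with inpatients does not show this. The weight in 11.1 would then carry the seasonality of all fever attendance into analyses of child outpatients or adult outpatients alone. The protocol itself expects the causes of fever to differ between children and adults, so a common seasonal pattern cannot be taken for granted.

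For incidence, the numerator is restricted by residence and the tally is not. The AFs that multiply fever incidence are specific to age stratum and outpatient status, and the tally is specific to neither. At two of the five sites the word hospital, taken literally, leaves out facilities where outpatients are enrolled.

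The weighting for primary objective 1 and the burden estimates of secondary objective 1 are at stake. A statistical analysis plan can refine a definition, but it cannot recover counts that were never tallied.

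**Working it through.** The plan gives no figure for either quantity, so there is none to reproduce. The quota does agree with the sample size: 12 × 50 weeks = 600 and 12 × 52 weeks = 624 per category, against a target of 600. I therefore take the fixed quota as the real sampling scheme.

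**1. What each use needs, and what 7.2.1 names**

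| Use | Needed | Named in 7.2.1 |
|---|---|---|
| Weight for outpatient AF by age stratum | Total presenting, by age group and outpatient status, per season | One total per day or week |
| Incidence numerator | Cases resident in the defined population | No residence for presenters who were not screened |
| Either, in Mozambique and Zimbabwe | All enrolling facilities | The hospital |

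**2. Weights**

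Take two seasons with equal enrolment, as the quota implies, and weight each season by total presenting over enrolled. Let R be the stratum's own wet:dry ratio of cases, and T the ratio in the pooled total.

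- Correct weighted prevalence = (R × p_wet + p_dry)/(R + 1).
- With the pooled total, T replaces R.

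The protocol gives no seasonal figures, so p_wet = 20%, p_dry = 5% and all the ratios are assumptions.

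| R | T | Correct | With pooled total | Factor |
|---|---|---|---|---|
| 3 | 1.5 | (0.60 + 0.05)/4 = 16.3% | (0.30 + 0.05)/2.5 = 14.0% | 0.86 |
| 2 | 1.2 | (0.40 + 0.05)/3 = 15.0% | (0.24 + 0.05)/2.2 = 13.2% | 0.88 |
| 1 | 2 | (0.20 + 0.05)/2 = 12.5% | (0.40 + 0.05)/3 = 15.0% | 1.20 |
| 2 | 2 | 15.0% | 15.0% | 1.00 |

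The error can go either way, and it vanishes when R = T. The difference in level between categories does not matter here. If every weight in a stratum is multiplied by the same constant, the constant cancels from numerator and denominator.

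**3. Incidence**

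- Outpatients only: with the protocol's own 80% share, all-comer count / in-area count = 1/0.80 = 1.25.
- Inpatients in the same total: let f be the inpatient share of the count and s the share of inpatients living in the area. The in-area share is (1 − f) × 0.80 + f × s. With assumed f of 5% to 30% and s of 30% to 80%, the extremes are 1/0.80 = 1.25 (s = 80%, any f) and 1/(0.70 × 0.80 + 0.30 × 0.30) = 1/0.65 = 1.54.

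These factors apply only if the tally is used without adjustment. In Mozambique and Zimbabwe, leaving out the posts or clinics would pull the count the other way. The documents do not give the hospital's share of attendances there, so the net direction at those two sites is unknown.

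**The case against.** A reader might infer that neither the weights nor incidence can be computed at all. The protocol does not support that.

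- **Weights.** Section 11.1 literally asks for the total seen at the study site in the season. A daily or weekly total gives exactly that at the three single-hospital sites. The defect is that this definition does not fit the outpatient, age-stratified analysis that it serves.
- **Incidence.** Section 7.5.4 asks only for an estimate. Residence is recorded for patients who are screened and excluded, and section 6 makes residence in the catchment an enrolment criterion for outpatients. With consecutive recruitment and a rotating start day, the in-area share among screened patients can be estimated. However, the protocol states no such step, and combining categories still needs category totals, because the sampling fractions differ.
- **The 25%.** Section 11.1 limits the numerator to the defined population, so using the raw tally would depart from the plan. The figure is the price of making no adjustment, not a predicted bias.
- **Unequal sampling fractions.** A reader might also infer that very different sampling fractions in the four categories bias the AFs. They do not, because the AFs are estimated within strata and a constant cancels. Only seasonality matters.
- **Silence.** The text does not say that no breakdown is kept, and the screening forms in Appendix C are not shown. The word hospital may be loose, since 7.5.4 uses study sites and study hospital for the same method.

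All of this narrows the point. What stands is that the count, as specified, does not match its two uses, and that category or facility counts not taken at the time cannot be rebuilt later.

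**Conclusion.** The concern holds in a limited form. As written, the single total does not give weights matched to the analysis groups in 11.1. It gives the residence-restricted numerator only after a step that the protocol does not describe. Its wording also leaves the coverage of posts and clinics at two sites unclear.

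The weight error ranges from about −14% to +20% of the weighted prevalence in the scenarios shown. It is zero if every category shares one seasonal pattern, and its size rests wholly on assumed ratios and prevalences. The incidence factor of 1.25 rests on the protocol's 80% share and on use of the tally without adjustment. The range up to 1.54 adds assumed inpatient shares.

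This should be changed, because it is cheap to put right during recruitment and cannot be put right afterwards. It does not make either objective unattainable.

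**What to change.** **In 7.2.1:** keep the daily or weekly fever tally at every enrolling facility, split by the four existing recruitment categories (age under 15, or 15 and over; outpatient or inpatient).

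**In 11.1, weights:** define the sampling fraction as enrolled over total presenting within each analysis group and season.

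**In 11.1, incidence:** compute the numerator as the category tally times the in-area fraction among consecutively screened patients (enrolled plus excluded), by category and by month or season. Apply each stratum's AF to its own incidence.

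**Cost:** a four-column sheet at each facility and a small extra analysis step, with no new participant procedure. The in-area fraction has sampling error, which must be carried into the incidence interval. As a guide, suppose 80% live in the area and residence is the only ground for exclusion (assumption). Enrolling 600 then means screening about 600/0.80 = 750, and the 95% half-width over the year is 1.96 × √(0.80 × 0.20/750) = 2.9 percentage points. For one month (600/12 = 50 enrolled, 50/0.80 = 62.5 screened) it is 1.96 × √(0.16/62.5) = 9.9 points, so season may be the better unit than month.

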7.2.2 Provision of written informed consent and assent

Written informed consent forms and information sheets on study participation (Appendices A and B) will be provided for each adult participant (over the age of majority according to local regulations for each site) or parent/guardian (for younger participants) at the time of enrolment. A trained study staff member will conduct individual screening interviews and informed consent discussions with potential study participants and parents/guardians. Informed consent will be conducted in the potential participant/parent/guardian's preferred language, with the assistance of a translator if necessary. Consent forms, approved by all relevant ethical review boards, will be available in English (Laos, Malawi, Myanmar, Zimbabwe) or Portuguese (Mozambique) and in the local language/s for each site.

If an adult or parent/guardian consents to participation but is unable to write, her/his fingerprint will be substituted for a signature, and a signature from an impartial adult witness to the informed consent procedures will be obtained. For participants under the age of adulthood at each site, country-specific guidelines on the inclusion of minors in research (including guidelines related to consent from a parent or guardian, and/or emancipated minors) will be followed. In particular, in addition to parent/guardian consent, assent will be sought for participants under the adult age, according to local regulations and recommendations for each study site. If a patient is severely ill and unable to give consent or

assent at the time of enrolment, their next of kin (parent or guardian in the case of a minor, spouse in the case of married individuals, etc, will be asked to provide informed consent on behalf of the patient. If/when the participant regains capacity to make their own decisions, they will be asked to confirm or withdraw their informed consent, with care taken to ensure they understand that they are free to withdraw from the study without risk of jeopardizing their access to current or future routine health care.

Potential participants and/or their parents/guardians will have the opportunity to ask questions and discuss details of the study with study staff, and are free to ask further questions at any time during or after completion of the study activities. If the participant meets all study enrolment criteria, s/he will be enrolled (Appendix C). At enrolment, each participant's contact information (telephone number and place of residence) will be recorded. This information will be kept in locked files, separately from study data files, until completion of reference lab testing (section 7.6) so that participants can be contacted if needed for clinical or study follow-up purposes.

7.3 Study activities and data collection at the time of patient enrolment

7.3.1 Clinical and demographic data collection

At enrolment of each participant, study staff will collect basic demographic data (age, sex, place of residence, ethnicity) and information on the history of the present illness (including presence and duration of symptoms, current and past health history, immunization and recent treatment history, recent specific exposures). A study staff clinician will perform a physical examination including symptoms and signs for assigning a standardized severity score (e.g., FEAST Paediatric Emergency Triage [PET]²⁵ or Lambaréné Organ Dysfunction Score [LODS]^{26,27} for children aged <15 years and quick Sequential Organ Failure Assessment [qSOFA]²⁸⁻³⁰ or another “universal vital assessment” [UVA]³¹ score for older patients; see sample data collection form, Appendix D).

